8.1.4 Other Procedures

Withdrawal/Discontinuation

When a subject discontinues/withdraws prior to trial completion, all applicable activities scheduled for the final trial visit should be performed at the time of discontinuation. Any adverse events which are present at the time of discontinuation/withdrawal should be followed in accordance with the safety requirements outlined in Section 8.2 - Assessing and Recording Adverse Events. Subjects who a) attain a CR or b) complete 24 months of treatment with nivolumab and metformin combination may discontinue treatment with the option of restarting treatment if they meet the criteria specified in Section 8.1.7.2. After discontinuing treatment following assessment of CR, these subjects should return to the site for a Safety Follow-up Visit (described in Section 8.1.6) and then proceed to the Follow-Up Period of the study (described in Section 8.1.7).

8.1.5 Visit Requirements

Visit requirements are outlined in Section 7.0 - Trial Flow Chart. Specific procedure-related details are provided above in Section 8.0 - Trial Procedures.

8.1.5.1 Screening

Screening Period

All subjects must sign an informed consent document prior to the initiation of any study related procedures. The informed consent document must be signed within 28 days of Cycle 1 Day 1. Screening procedures are to be conducted within 28 days of Cycle 1 Day 1.

- Review of study eligibility criteria
- Medical History
- Record concomitant medications taken up to 28 days prior to day 1 cycle 1
- Vitals [temperature, heart rate (HR), blood pressure (BP) and respiratory rate (RR)]
- Physical Examination, including height and weight
- ECOG Performance Status evaluation (within 14 days or less of cycle 1 day 1)
- Laboratory Assessments

- Hematology: hemoglobin, hematocrit, red blood cell count, white blood cell count with differential and platelet count
- Serum chemistry: sodium, potassium, chloride, bicarbonate, magnesium, calcium, phosphorus, blood urea nitrogen, creatinine, total bilirubin, LDH, total protein, ALP, ALT, AST, and albumin. Fasting triglycerides, cholesterol and glucose.
- Serum or urine pregnancy test for women of childbearing potential. Must be within 72 hours of study drug
- Prothrombin time (PT) and activated partial thromboplastin time (aPTT)
- Urinalysis
- Tumor markers: CEA
- T3, FT4, TSH
- 12-lead ECG
- Radiologic imaging studies to evaluate tumor status. contrast computed tomography (CT) or magnetic resonance imaging (MRI) of the chest and abdomen and pelvis. Additional imaging may be obtained as clinically indicated. Baseline scans may be done within 4 weeks prior to cycle 1 day 1.
- Baseline fresh biopsy (in all patients, 28 total) will be obtained within 28 days of day 1 cycle 1 and after consent is signed.
- Blood sample 20 cc for correlative work

8.1.5.2 Treatment Period

8.1.5.3 Lead in Cycle 1 Day -14

- Record concomitant medications
- Vitals (temperature, HR, BP and RR)
- History and physical exam, pill diary and pill count, blood glucose log for diabetic patients
- ECOG performance status
- Toxicity assessment
- Laboratory Assessments
 - Hematology hemoglobin, hematocrit, red blood cell count, white blood cell count with differential and platelet count
 - Chemistry sodium, potassium, chloride, bicarbonate, magnesium, calcium, phosphorus, blood urea nitrogen, creatinine, glucose (random), total bilirubin, LDH, total protein, ALP, ALT, AST, and albumin
 - For the cycle1 day -1 labs, lab results from the screening tests maybe used if completed within 1 week of day -1

- Tumor marker – CEA
- Metformin

8.1.5.4 Cycle 1 Day -7 phone call

- Metformin
- Review of adverse events, dosing compliance and concomitant medication (by clinical trial coordinator via phone call)

8.1.5.5 Cycle 1 Day 1

- Record concomitant medications
- Vitals (temperature, HR, BP and RR)
- History and physical exam, pill diary and pill count, blood glucose log for diabetic patients
- ECOG performance status
- Toxicity assessment
- Laboratory Assessments
 - Hematology hemoglobin, hematocrit, red blood cell count, white blood cell count with differential and platelet count
 - Chemistry sodium, potassium, chloride, bicarbonate, magnesium, calcium, phosphorus, blood urea nitrogen, creatinine, glucose (random), total bilirubin, LDH, total protein, ALP, ALT, AST, and albumin
- Blood sample 20 cc for correlative work
- **Subject# 1-9, 19-23** (14 patients in total) will get biopsy#2 of paired biopsy (same day or up to 5 days later)
- Continue metformin
- Nivolumab will be started after biopsy#2 (same day or up to 5 days later).
- Nivolumab 480 mg will be administered as a 30-minute IV infusion in the infusion center. Given the variability of infusion pumps, a window of -5 minutes and +10 minutes is permitted (i.e., infusion time is 30 minutes: -5 min/+10 min).

8.1.5.6 Cycle 1 Day 15

- Record concomitant medications
- Vitals (temperature, HR, BP and RR)
- History and physical exam, pill diary and pill count, blood glucose log for diabetic patients
- ECOG performance status

- Toxicity assessment
- Laboratory Assessments
 - Hematology hemoglobin, hematocrit, red blood cell count, white blood cell count with differential and platelet count
 - Chemistry sodium, potassium, chloride, bicarbonate, magnesium, calcium, phosphorus, blood urea nitrogen, creatinine, glucose (random), total bilirubin, LDH, total protein, ALP, ALT, AST, and albumin
 - Tumor marker – CEA
- Blood sample 20 cc for correlative work
- The second half of the patients **Subject #10-18, 24-28** (14 patients in total) will get biopsy#2 of paired biopsy (same day or up to 5 days later)
- Continue metformin

8.1.5.7 Cycle 2 Day 1

- Record concomitant medications
- Vitals (temperature, HR, BP and RR)
- History and physical exam, pill diary and pill count
- ECOG performance status
- Toxicity assessment
- Laboratory Assessments
 - Hematology hemoglobin, hematocrit, red blood cell count, white blood cell count with differential and platelet count
 - Chemistry sodium, potassium, chloride, bicarbonate, magnesium, calcium, phosphorus, blood urea nitrogen, creatinine, glucose (random), total bilirubin, LDH, total protein, ALP, ALT, AST, and albumin
 - Tumor marker – CEA (every 2 cycles after cycle 2)
 - T3, FT4, TSH at cycle 2 and then after every 3 cycles
- Metformin and Nivolumab combination
- Cross sectional imaging (CT or MRI) for restaging at the end of C#2 (\pm 3 days), then repeat every 2 cycles (every 8 weeks)

8.1.5.8 Cycle 3 Day 1 and Day 1 of each subsequent cycle

- Record concomitant medications
- Vitals (temperature, HR, BP and RR)
- History and physical exam, pill diary and pill count
- ECOG performance status

- Toxicity assessment
- Laboratory Assessments
 - Hematology hemoglobin, hematocrit, red blood cell count, white blood cell count with differential and platelet count
 - Chemistry sodium, potassium, chloride, bicarbonate, magnesium, calcium, phosphorus, blood urea nitrogen, creatinine, glucose (random), total bilirubin, LDH, total protein, ALP, ALT, AST, and albumin
 - Fasting triglycerides, cholesterol and glucose (Cycle#3 and every 3 cycles)
 - Urinalysis (Cycle#3 and every 3 cycles)
- Metformin and Nivolumab combination
- Blood sample 20 cc for correlative work

8.1.5.9 End of treatment visit

- Record concomitant medications
- Vitals (temperature, HR, BP and RR)
- History and physical exam
- ECOG performance status
- Toxicity assessment
- Laboratory Assessments
 - Hematology hemoglobin, hematocrit, red blood cell count, white blood cell count with differential and platelet count
 - Chemistry sodium, potassium, chloride, bicarbonate, magnesium, calcium, phosphorus, blood urea nitrogen, creatinine, glucose (random), total bilirubin, LDH, total protein, ALP, ALT, AST, and albumin
 - Tumor markers - when applicable.
 - Urinalysis
 - T3, FT4, TSH
- Blood sample 20 cc for correlative work

8.1.6 Safety Follow-Up Visit

The mandatory Safety Follow-Up Visit should be conducted approximately 30 days after the last dose of trial treatment or before the initiation of a new anti-cancer treatment, whichever comes first. All AEs that occur prior to the Safety Follow-Up Visit should be recorded. Subjects with an AE of Grade > 1 will be followed until the resolution of the AE to Grade 0-1 or until the beginning of a new anti-neoplastic therapy, whichever occurs first. SAEs that occur within 90 days of the end of treatment or before initiation of a new anti-cancer treatment should also be followed and recorded. Subjects who are eligible for retreatment with nivolumab/metformin (as described in

Section 8.1.7.2) may have up to two safety follow-up visits, one after the Treatment Period and one after the Second Course Phase.

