8.2.1.1 Reporting of Serious Adverse Events Associated with Nivolumab

- All Serious Adverse Events (SAEs) that occur following the subject's written consent to participate in the study through 100 days for nivolumab or discontinuation of dosing must be reported to BMS Worldwide Safety, whether related or not related to study drug. If applicable, SAEs must be collected that relate to any later protocol-specified procedure (eg, a follow-up skin biopsy).
- Following the subject's written consent to participate in the study, all SAEs, whether related or not related to study drug, are collected, including those thought to be associated with protocol-specified procedures. The investigator should report any SAE occurring after these aforementioned time periods, which is believed to be related to study drug or protocol-specified procedure to BMS.
- An SAE report should be completed for any event where doubt exists regarding its seriousness;
- If the investigator believes that an SAE is not related to study drug, but is potentially related to the conditions of the study (such as withdrawal of previous therapy or a complication of a study procedure), the relationship should be specified in the narrative section of the SAE Report Form.

An appropriate SAE form (e.g. ex-US = CIOMS form or USA = Medwatch form) should be used to report SAEs to BMS. If you prefer to use your own Institutional form, it must be reviewed by the BMS Protocol Manager prior to study initiation to ensure that at a minimum all of the data elements on the CIOMS form are present. Note: Please include the BMS Protocol number on the SAE form or on the cover sheet with the SAE form transmission.

- - ✓ The CIOMS form is available at: <http://www.cioms.ch/index.php/cioms-form-i>
 - ✓ The MedWatch form is available at: [MedWatch 3500 Form](#)
- The Sponsor-investigator will reconcile the clinical database AE cases (**case level only**) transmitted to BMS Global Pharmacovigilance ([contact]).
 - The Investigator will request from BMS GPV&E, [contact] the SAE reconciliation report and include the BMS protocol number every 3 months and prior to data base lock or final data summary
 - GPV&E will send the investigator the report to verify and confirm all SAEs have been transmitted to BMS GPV&E.

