8.2.2.1 Non-serious Adverse Event Collection and Reporting

The collection of non-serious AE information should begin at initiation of study drug. All non-serious adverse events (not only those deemed to be treatment-related) should be collected continuously during the treatment period and for a minimum of 100 days for nivolumab following the last dose of study treatment.

Non-serious AEs should be followed to resolution or stabilization, or reported as SAEs if they become serious. Follow-up is also required for non-serious AEs that cause interruption or discontinuation of study drug and for those present at the end of study treatment as appropriate.

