The DSMC will render a recommendation and rating based on the overall trial conduct. The PI is responsible for ensuring that instances of egregious data insufficiencies are reported to the IRB. Continuing Review submissions will include the DSMC recommendation letter. Should any revisions be made to the protocol-specific monitoring plan after initial DSMC approval, the PI will be responsible for notifying the DSMC of such changes. The Committee reserves the right to conduct additional audits if necessary.

[name] and the investigators, the clinical research coordinator and the regulatory affairs coordinator will meet to review and discuss study data to ensure subject safety weekly. During the meetings the PI or co-I will review the eligibility criteria for each new patient. In addition, during these meeting the group will review all the toxicity (AE/SAE) logs, random checks of case report form completion and roadmap for each patient on the trial. All study personnel will be trained on the protocol by the PI or co-I. Study personnel will sign training log prior to being included on delegation of authority log. All AE and SAE will be handled according to Section 8.2 which provides detailed instructions on reporting requirements.

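### Section 8.1.6 sets shorter adverse-event windows than Section 8.2, and after the day-30 visit no planned contact asks patients in survival follow-up without ongoing toxicity about new events

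*Combined protocol and SAP*

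**What the plan says.** Section 8.1.6 (Safety Follow-Up Visit) places a mandatory visit at about 30 days after the last dose, or before new anti-cancer treatment if that comes sooner. It then gives three rules:

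- For adverse events generally: "All AEs that occur prior to the Safety Follow-Up Visit should be recorded".
- For serious events, follow-up and recording of "SAEs that occur within 90 days of the end of treatment or before initiation of a new anti-cancer treatment".
- Events above Grade 1 are followed to Grade 0-1 or "until the beginning of a new anti-neoplastic therapy, whichever occurs first".

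Section 8.2 is different on each count:

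- Under 8.2.2.1, all non-serious events are collected during treatment and "for a minimum of 100 days for nivolumab following the last dose of study treatment". It adds: "Non-serious AEs should be followed to resolution or stabilization".
- Under 8.2.1.1, all SAEs from consent "through 100 days for nivolumab or discontinuation of dosing must be reported to BMS Worldwide Safety". For later events believed related to study drug or a protocol procedure: "The investigator should report any SAE occurring after these aforementioned time periods".

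Neither rule in 8.2 stops at progression or at new therapy. On precedence, Section 11.5 says "All AE and SAE will be handled according to Section 8.2", and 8.1.2.1 also refers the reader to 8.2 for assessing and recording events.

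The contacts after treatment are these. Under 8.1.7, patients who stop for a reason other than progression are assessed every 8 weeks by imaging. Under 8.1.1.5 and 8.1.7.1, patients who progress or start new therapy move to a telephone call every 12 weeks, and its stated purpose is survival status. Footnote b of the Section 7 calendar limits the Follow Up Visits to patients whose treatment-related toxicity is still ongoing.

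**The concern.** Section 6.2.2 warns that nivolumab's immune-type events can first appear months after dosing has ended. The stretch after day 30 is therefore one in which new drug-related events are expected.

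Take a patient who stops at progression, attends the day-30 visit with no outstanding toxicity, and develops a first non-serious immune event on day 60. Section 8.2.2.1 requires that event to be collected. Section 8.1.6, read on its own, tells site staff that recording ended at the visit. The only contact planned for this patient is a call about survival. The event may then be missing from the Section 10.6.1 summaries of related events and, if it is Grade 3 or above but not serious, from the summary of severe events. Section 10.6.1 does not say which window its tables cover, so a reader of the results could not tell.

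This is a weakness in data collection. It does not touch the response-rate endpoint or the two-stage rule.

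**Working it through.** The plan states no figure to reproduce. The check sets the windows side by side and then asks which planned contacts could fill the difference.

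**Windows, in days after the last dose**

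| Item | 8.1.6 | 8.2 | Difference |
|---|---|---|---|
| Non-serious AEs | about 30, or earlier at new therapy | at least 100 | 100 − 30 = 70 |
| SAEs | 90 | 100, plus later related SAEs | 100 − 90 = 10 |
| Follow-up of existing events | events above Grade 1 stop at new therapy | non-serious events until they resolve or stabilize | no fixed number of days |

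The 70 days becomes longer if new therapy brings the safety visit forward.

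**Contacts after the safety visit**

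- *Stopped for a reason other than progression, no new therapy (8.1.7).* Assessments every 8 weeks fall at 8 × 7 = 56 and 16 × 7 = 112 days. With the ±7-day window the second falls between days 105 and 119, so an adverse-event review at that visit would cover day 100.
- *Progressed or started new therapy (8.1.1.5, 8.1.7.1).* Calls every 12 weeks, for survival status. In the calendar as extracted, the adverse-event review row is marked at discontinuation, at day 30 and at the 8-weekly visits, and is blank under Survival Follow-Up. The extracted columns may be shifted (a physical examination is marked under what is a telephone contact), so the argument rests on the text of 8.1.7.1, not on the table.

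**When the first survival call falls**

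Section 8.1.7.1 gives an interval of 12 × 7 = 84 days but no starting point. Three assumptions give a range:

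1. Counted from discontinuation, with the last metformin dose on that day: day 84. That is 100 − 84 = 16 days before the window closes.
2. Counted from progression found at an end-of-cycle scan, with day 0 set at the last nivolumab dose on Day 1 of that 28-day cycle: 28 + 84 = day 112, or 109 to 115 with the ±3-day scan window. That is 112 − 100 = 12 days after the window closes.
3. Counted from the day-30 visit: 30 + 84 = day 114, which is 114 − 100 = 14 days after it closes.

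Under all three a call falls near day 100, but its stated content is survival only.

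**Size of the loss**

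The number of events missed cannot be computed: the documents give neither a rate of late non-serious immune events nor the share of patients who would take this route.

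**The case against.** The best reply is that Section 8.2 governs. It requires continuous collection for at least 100 days, 8.1.2.1 and 11.5 both point to it, and 8.1.6 does not forbid later recording. Section 11.5 also has the team review toxicity logs weekly. Section 6.4 asks for concomitant medications given more than 30 days after the last dose to be recorded for SAEs and events of clinical interest, so the plan clearly expects some events after day 30. All of this stands, and it means the duty to collect exists. It does not supply an occasion on which the patient is asked, and a log review can only examine what has been entered.

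Four stronger readings are tempting and are not supported:

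- *That these patients have no safety contact at all after day 30.* Footnote b, read alone, does not exclude a patient who has progressed but still has treatment-related toxicity. Section 6.9 follows patients removed for unacceptable adverse events until the event resolves or stabilizes. The gap concerns new events in patients without such toxicity.
- *That the SAE window in 8.1.6 ends early at new therapy.* The SAE sentence joins its two limits without saying that the earlier one applies, although the same paragraph does say so for the visit and for follow-up above Grade 1. Only the 10-day difference is secure.
- *That a late event is recorded only if the patient volunteers it.* The continuous-collection duty in 8.2.2.1 allows other routes.
- *That footnote b contradicts 8.1.7.* This is probable but not certain: 8.1.7 is about imaging for disease status, and the footnote may restrict only the clinical toxicity visit.

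**Conclusion.** The point holds as a minor inconsistency in data collection. Section 8.1.6 states windows shorter than those of Section 8.2, by about 70 days for non-serious events and 10 days for SAEs, and it ends follow-up above Grade 1 at new therapy where 8.2.2.1 does not. Even with Section 8.2 governing, a patient who has progressed or started new therapy and has no ongoing treatment-related toxicity has no planned contact after the safety visit at which new events are asked about. New non-serious immune events from about day 30 to day 100 may therefore be under-recorded.

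The mismatch in the text is certain. The under-recording is a possibility of unknown size. It rests on reading the survival calls as limited to survival status, which is what 8.1.7.1 says.

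A reader might infer that serious immune events would be lost or that the trial's conclusion is at risk. Neither follows: 8.2.1.1 requires all SAEs through 100 days and related ones afterwards, and no decision rule uses these data.

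**What to change.** 1. **Section 8.1.6.** Record AEs and SAEs with onset up to 100 days after the last dose, and follow them as in Section 8.2, with no stop at new therapy. Keep the day-30 visit. State which drug's last dose starts the clock; 8.2.2.1 names nivolumab but counts from the last dose of study treatment.
2. **Section 8.1.7.1 and the Section 7 calendar.** Schedule the first survival call at or shortly after day 100, and add an adverse-event review covering the time since the last such assessment. A patient still in the 8-weekly phase can have this at the visit around day 112. Clarify that footnote b does not remove the 8.1.7 visits from patients who stop for reasons other than progression.
3. **Section 10.6.1.** Tabulate adverse events through 100 days after the last dose, flagging those with onset after new anti-cancer therapy.

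The cost is a few text edits and some extra questions on a call already planned, which would move by roughly 12 to 16 days depending on the starting point now intended. No visit or test is added. There are limits. Attribution is harder once new therapy has begun, which is why those events are flagged. A telephone call may still miss laboratory-only events such as thyroid changes. Patients already past day 100 can only be asked in retrospect.

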8.1.7 Follow-up Visits

Subjects who discontinue trial treatment for a reason other than disease progression will move into the Follow-Up Phase and should be assessed every 8 weeks (\pm 7 days) by radiologic imaging to monitor disease status. After 1 year, the imaging time point will occur every 9 weeks (\pm 7 days). Every effort should be made to collect information regarding disease status until the start of new anti-neoplastic therapy, disease progression, death, end of the study or if the subject begins retreatment with nivolumab and metformin as detailed in Section 7.1.6.2. Information regarding post-study anti-neoplastic treatment will be collected if new treatment is initiated. Details are provided in Section 7.0 – Trial Flow Chart.

8.1.7.1 Survival Follow-up

Once a subject experiences confirmed disease progression or starts a new anti-cancer therapy, the subject moves into the survival follow-up phase and should be contacted by telephone every 12 weeks to assess for survival status until death, withdrawal of consent, or the end of the study, whichever occurs first.

8.1.7.2 Second Course Phase (Retreatment Period)

Subjects who stop nivolumab/metformin with SD or better may be eligible for up to one year of additional nivolumab/metformin therapy if they progress after stopping study treatment. This retreatment is termed the Second Course Phase of this study and is only available if the study remains open and the subject meets the following conditions:

- **Either**

- Stopped initial treatment with nivolumab/metformin after attaining an investigator-determined confirmed CR according to RECIST 1.1, and
 - Was treated for at least 24 weeks with nivolumab/metformin before discontinuing therapy
 - Received at least two treatments with nivolumab/metformin beyond the date when the initial CR was declared

OR

- Had SD, PR or CR and stopped nivolumab/metformin treatment after 24 months of study therapy for reasons other than disease progression or intolerance

AND

- Experienced an investigator-determined confirmed radiographic disease progression after stopping their initial treatment with nivolumab/metformin

- Did not receive any anti-cancer treatment since the last dose of nivolumab/metformin
- Has a performance status of 0 or 1 on the ECOG Performance Scale
- Demonstrates adequate organ function as detailed in Section 5.1.7
- Female subject of childbearing potential should have a negative serum or urine pregnancy test within 72 hours prior to receiving retreatment with study medication.
- Female subject of childbearing potential should be willing to use 2 methods of birth control or be surgically sterile, or abstain from heterosexual activity for the course of the study through 120 days after the last dose of study medication (Reference Section 5.1.10). Subjects of child bearing potential are those who have not been surgically sterilized or have been free from menses for > 1 year.
- Male subject should agree to use an adequate method of contraception starting with the first dose of study therapy through 120 days after the last dose of study therapy.
- Does not have a history or current evidence of any condition, therapy, or laboratory abnormality that might interfere with the subject's participation for the full duration of the trial or is not in the best interest of the subject to participate, in the opinion of the treating investigator.

Subjects who restart treatment will be retreated at the same dose and dose interval as when they last nivolumab/metformin. Treatment will be administered for up to one additional year.

Visit requirements are outlined in Section 7.0 – Trial Flow Chart

